10.7.1 Whole Body Radiation Exposure

In the current study, all patients will have whole body radiation doses calculated based on serial measurements of radiation exposure rate with an ionization chamber set at a fixed distance and geometry. Our primary analyses will compare whole body radiation dose between randomized treatment groups and also between responders vs. non-responders using analysis of variance. Secondary analyses will compare whole body radiation dose between patients with and without grade 4 neutropenia, grade 4 thrombocytopenia, and grade ≥ 3 non-hematologic toxicity.

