2.0 BACKGROUND

2.1 Neuroblastoma

Neuroblastoma is the most common extracranial solid cancer of childhood.¹ Most patients are initially diagnosed prior to 10 years of age. Approximately 50% of patients present with initially metastatic disease. Many of these patients are either refractory to initial therapy or develop recurrent disease after receiving multimodal therapy. The outcome for patients with recurrent or refractory disease remains poor. Novel approaches to treating these patients are required to improve their outcome.

2.2 ¹³¹I-MIBG: Clinical Data in Neuroblastoma

¹³¹I-metaiodobenzylguanidine (MIBG) is a guanethidine analog with specific uptake in sympathetic nervous system tissues. The norepinephrine transporter mediates uptake of ¹³¹I-MIBG into the cells of these tissues.² As a tumor derived from the sympathetic nervous system, neuroblastoma cells avidly accumulate ¹³¹I-MIBG.³⁻⁵ Low doses of both ¹³¹I-MIBG and ¹²³I-MIBG are widely used as nuclear medicine imaging agents in the diagnostic evaluation of patients with neuroblastoma.

Given that neuroblastoma is radiosensitive, high-dose ¹³¹I-MIBG has been evaluated as a targeted radiopharmaceutical in the treatment of patients with neuroblastoma for the past 25 years. Unlike standard external beam radiotherapy, ¹³¹I-MIBG is administered intravenously and then distributes throughout the body.⁶ The biological or effective half-life of the administered radiation in the blood of patients with neuroblastoma ranges from 9-130 hours, reflecting clearance mainly in the urine.⁶⁻⁸ Radiation that is not cleared in the urine or stool remains in the body and decays with a half-life of approximately 8 days, the physical half-life of ¹³¹I.⁹ Since ¹³¹I-MIBG taken up by neuroblastoma cells is not cleared in the urine or stool, these cells are exposed to radiation with a half-life that more closely follows the physical half-life of ¹³¹I. Therefore, three weeks following therapeutic ¹³¹I-MIBG administration, tumor cells may still be exposed to small amounts of radiation.

The whole body radiation dose received is approximately linear with ¹³¹I-MIBG dose administered. After a dose of 12 mCi/kg, patients receive a calculated whole-body radiation dose of approximately 2 Gy.¹⁰ As a targeted radiopharmaceutical, the dose delivered to the tumor is much higher.¹⁰

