2.6 Correlative and Exploratory Studies

2.6.1 Whole Body Radiation Exposure Following ¹³¹I-MIBG Therapy

Previous studies of therapeutic ¹³¹I-MIBG have derived estimates of whole body radiation exposure typically by using serial measurements of radiation exposure rate with an ionization chamber set at a fixed distance and geometry from the patient.¹⁰ Patients treated with doses ≥ 10 mCi/kg typically have estimated whole body radiation doses of ≥ 200 cGy.^{10, 90} In a group of 53 patients treated with 18 mCi/kg ¹³¹I-MIBG, the median estimated whole body radiation dose was 292 cGy, with a broad range of 173 – 418 cGy.¹² Higher whole body radiation dose appears to correlate with increased hematologic toxicity^{10, 12, 90}, though the impact of whole body radiation dose on response to ¹³¹I-MIBG therapy remains unclear.¹⁰ Moreover, it is not clear whether the addition of irinotecan or vorinostat might impact whole body radiation dose. Two potential mechanisms by which these agents might impact whole body radiation dose include increasing tumor uptake and/or retention of ¹³¹I-MIBG or by delaying physiologic clearance of ¹³¹I-MIBG.

In the current study, all patients will have whole body radiation doses calculated based on serial measurements of radiation exposure rate with an ionization chamber set at a fixed distance and geometry. The primary analyses will compare whole body radiation dose between randomized treatment groups and also between responders vs. non-responders. Secondary analyses will compare whole body radiation dose between patients with and without grade 4 neutropenia, grade 4 thrombocytopenia, and grade ≥ 3 non-hematologic toxicity.

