4.2.3.1 Vorinostat

Patients will receive vorinostat 180 mg/m²/dose (maximum dose 400 mg) once daily by mouth, NG, or G-tube on days -1 to +12 (14 total doses).

Vorinostat will be given for 14 days continuously, even if the ¹³¹I-MIBG portion of therapy is delayed due to production or other logistical reasons.

For patients unable to swallow capsules, vorinostat will be given as a 50 mg/mL extemporaneous liquid suspension (see section 6.1 for preparation instructions) with dosing according to the nomogram in Appendix III. The maximum absolute vorinostat dose is 400 mg.

Patients who are able to swallow capsules may receive vorinostat capsules instead of suspension if their calculated vorinostat dose is within +/- 10% of a 100 mg increment (eg. 100 mg, 200 mg, 300 mg, or 400 mg). Otherwise, they will need to receive vorinostat as suspension and dosed according to the nomogram in Appendix III. The maximum absolute vorinostat dose is 400 mg.

Vorinostat should be taken with food or within 30 minutes after a meal. The dose should be taken in the morning whenever possible.

On day 1 of therapy, vorinostat should be taken 1 hour prior to the start of the ¹³¹I-MIBG infusion. Note that patients on this arm of the trial are to have a BUN and Cr obtained on day 1 prior to the ¹³¹I-MIBG infusion to confirm that Cr still meets eligibility criteria in 3.2.10.2. See 4.8.1.5 for guidelines.

4.3 ¹³¹I-MIBG Administration for All Treatment Arms

The primary ¹³¹I-MIBG supplier for this study is Nuclear Diagnostics Products NDP. If a supply of ¹³¹I-MIBG is not available from NDP for a specified date, Jubilant DraxImage, Canada is a secondary ¹³¹I-MIBG supplier for this study.

4.3.1 ¹³¹I-MIBG Dose and Administration

¹³¹I-MIBG 18 mCi/kg is given on day 1 of therapy to all patients regardless of randomized treatment arm.

The maximum absolute dose of ¹³¹I-MIBG on this protocol is 1200 mCi, though individual MIBG treating centers may have lower maximum allowed doses due to radiation safety considerations.

The dose administered should be within 15% of the prescribed dose (see section 10.3.1 for definition of evaluable for response based upon administered ¹³¹I-MIBG dose). There will be no adjustment for obesity except to cap the absolute dose at 1200 mCi.

¹³¹I-MIBG is provided by both suppliers with a specific activity not less than 30 mCi/mg MIBG at the calibration date.

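### The comparison of whole-body radiation dose between arms (10.7.1) ignores administered mCi/kg and so gives up a small to moderate amount of precision

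*Combined protocol and SAP*

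**What the plan says.** Aim 1.5 (section 1.0, exploratory) is to compare whole-body radiation exposure across the three regimens. Section 10.7.1 gives the method: "Our primary analyses will compare whole body radiation dose between randomized treatment groups and also between responders vs. non-responders using analysis of variance". No covariate is named there. Section 10.7.3 adds a model with whole-body exposure as outcome by arm, and logistic models of response with arm, disease status and whole-body exposure among the covariates. Administered activity appears in none of these. The introduction to section 10.7 calls the correlative biology studies descriptive.

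On what determines the dose, section 2.2 says: "The whole body radiation dose received is approximately linear with ¹³¹I-MIBG dose administered". Section 4.3.1 fixes one prescription: "¹³¹I-MIBG 18 mCi/kg is given on day 1 of therapy to all patients regardless of randomized treatment arm". It then allows variation: "The dose administered should be within 15% of the prescribed dose", and "The maximum absolute dose of ¹³¹I-MIBG on this protocol is 1200 mCi, though individual MIBG treating centers may have lower maximum allowed doses". Section 2.6.1 reports, for 53 patients treated at 18 mCi/kg, that "the median estimated whole body radiation dose was 292 cGy, with a broad range of 173 – 418 cGy".

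**The concern.** If whole-body dose rises in proportion to administered activity, and activity per kg differs between patients, then an analysis of variance on raw cGy counts those differences as noise. The quantity that explains them is recorded anyway: section 10.3.1 needs administered against prescribed activity to judge evaluability, and weight is in the section 7.1 schedule. Section 2.6.1 suggests that a sensitizer might act through tumor uptake or retention, or through slower clearance. These mechanisms alter dose per unit of activity, so removing activity variation would sharpen the arm comparison.

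The comparison of responders with non-responders is not randomized. A difference in whole-body dose there could partly reflect who received more activity per kg. It could also reflect treatment arm, which the trial hypothesizes affects response and which might affect whole-body dose. Section 10.7.1 adjusts for neither.

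**Working it through.** **1. The plan's own power figure.** No power is stated for 10.7.1. The nearest statement (10.7.3, blood biomarkers) is 91% for a 0.05-level F-test with 3 arms, 28 per arm and largest minus smallest mean of 1 SD. With means at −0.5, 0 and +0.5 SD, the noncentrality is 28 × 0.5 = 14 on 2 and 81 df, and power is 91.8%. The figure reproduces, so the same method is used below.

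**2. How far mCi/kg can move.** The cap binds above 1200/18 = 66.7 kg. It gives 1200/80 = 15 mCi/kg at 80 kg and 1200/100 = 12 at 100 kg. Below the cap, the tolerance allows ±15%.

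**3. Spread of whole-body dose (assumption).** The cited range is 418 − 173 = 245 cGy. The expected range of 53 normal values is 4.54 SD, so SD ≈ 245/4.54 = 54 cGy and CV ≈ 54/292 = 18.5%.

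**4. How much of that spread activity could explain.** A ±15% window around 292 cGy is 248 to 336 cGy, and 87.6/245 = 36% of the cited range. Most of the spread at a fixed prescription therefore has other sources.

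**5. Gain from adjustment.** Under proportionality, R² = (CV of administered mCi/kg / 0.185)², and the standard error shrinks by the factor √(1 − R²). The CV of administered mCi/kg is not in the documents, so a range is shown. The power column takes 35 per arm and a difference of 0.753 SD (about 41 cGy), which has 80% power unadjusted. The adjusted test has noncentrality 35 × 0.753²/2 ÷ (1 − R²) on 2 and 101 df.

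| Assumed spread of mCi/kg | R² | Standard error reduced by | Power (from 80%) |
|---|---|---|---|
| SD 2.5% | 0.02 | 1% | 81% |
| SD 5% | 0.07 | 4% | 83% |
| Uniform over ±15% (SD 8.7%) | 0.22 | 12% | 89% |
| SD 10% (some capped patients) | 0.29 | 16% | 92% |

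The result also depends on the assumed dose CV. For activity SDs of 2.5% to 10%, the reduction is about 1% to 25% if the dose CV is 15%, and 0.5% to 8% if it is 25%. If the cited spread is instead read as the spread at constant activity, R² at SD 10% is 0.10²/(0.10² + 0.185²) = 0.23, and the reduction is 12%.

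**6. Responders versus non-responders.** Trials were simulated with 105 patients and about 25% responding. Whole-body dose was linked to response only through administered mCi/kg, and the unadjusted test was at nominal 5%. Rejection rates by assumed odds ratio of response per 10% higher mCi/kg were:

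| Activity SD | OR 1.5 | OR 2 | OR 3 |
|---|---|---|---|
| 2.5% | 5% | 5% | 5% |
| 5% | 5% | 7% | 10% |
| 8.7% | 9% | 19% | 37% |

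The effect runs from negligible to material. Neither the activity spread nor the odds ratio is given in the documents.

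**The case against.** The strongest defense is that the planned analysis answers the stated aim. Aim 1.5 asks about exposure, which is total dose by regimen. Uptake, retention and clearance appear in section 2.6.1 only as possible mechanisms. Adjusting for activity, or dividing by it, asks about exposure per unit of activity. This stands, and it is why the unadjusted comparison must stay in the report.

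Also standing: all arms share one prescription; most of the 2.4-fold range seen at 18 mCi/kg is not due to administered activity; the work is exploratory; and no power claim in 10.7.1 fails.

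Three stronger readings are tempting, and the documents support none of them.

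- *The arm comparison is biased.* Patients are randomized to the same prescribed activity, so leaving out the covariate costs precision only.
- *The responder comparison is confounded.* Activity lies upstream of whole-body dose. If responders had more exposure because they received more activity, that is a real difference in exposure. Confounding needs activity, or something related to it, to affect response by another route, and no size for that is given. The one route visible in the text runs opposite to the simulated case: the cap lowers mCi/kg in heavier patients (older ones, by assumption), while section 2.2 says older patients respond more often.
- *Adjustment is worth about 28% to 42% more patients.* That is 1/(1 − R²) in the last two rows of the first table. The 15% is a tolerance, not an observed distribution, and the documents do not say how many patients reach the cap. The first two rows (2% and 8%) are equally compatible with the text.

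The defense does not answer the narrower point. The protocol names a predictor of this outcome, the trial records it, and no planned model uses it.

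**Conclusion.** The point holds as a minor improvement. The arm comparison in 10.7.1 is valid but less precise than it could be. The loss is about 1% to 16% of the standard error, assuming a whole-body dose CV near 18.5%, proportionality to activity, and an SD of administered mCi/kg between 2.5% and 10%. Only the proportionality has direct support in the text; the dose CV is inferred from a reported range, and the activity spread is assumed. For responders versus non-responders, administered activity may account for part of a difference. That justifies a sensitivity analysis, not replacing the planned one. Selection of the winning regimen is not touched.

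**What to change.** In section 10.7.1:

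- Add an analysis of covariance of whole-body dose by randomized arm, with administered mCi/kg (administered activity divided by actual body weight) as covariate.
- Report the planned analysis of variance alongside it and label it the total-exposure comparison.
- Tabulate the distribution of administered mCi/kg by arm.
- For responders versus non-responders, keep the unadjusted comparison and add a sensitivity model with treatment arm and administered mCi/kg.

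The cost is a change of wording and one degree of freedom for the covariate in the arm comparison; the data are already collected. There are two small drawbacks. The adjusted result concerns exposure per unit of activity. Administered activity is also known only after randomization, and could differ by arm if, for example, infusions are postponed under the Arm C creatinine rule in section 4.8.1.5. The table by arm would show this.

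Separately, section 4.3.1 rules out any obesity adjustment of the ¹³¹I-MIBG dose other than the cap, while Appendix VI allows that dose to be based on adjusted body weight. The two must be reconciled, because they bear on how mCi/kg is read in heavier patients. Using actual body weight for the covariate is an analysis definition only and does not favor either dosing text.

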While these combination trials have demonstrated promising antitumor activity, these small phase 1 studies have not clarified whether combination therapy results in increased response rates compared with single-agent ¹³¹I-MIBG. The current randomized phase 2 pick the winner study is therefore designed to select the ¹³¹I-MIBG treatment regimen associated with the highest objective response rate. Patients with relapsed or refractory neuroblastoma and MIBG-avid disease will be randomized at study entry to one of three treatment arms: single-agent ¹³¹I-MIBG; ¹³¹I-MIBG with vincristine and irinotecan; and ¹³¹I-MIBG with vorinostat. All patients will receive 18 mCi/kg ¹³¹I-MIBG with prophylactic autologous stem cell support two weeks following ¹³¹I-MIBG infusion. Patients enrolling prior to Amendment 7A may receive up to two courses of therapy. Patients enrolling with Amendment 7A and after may receive only one course of therapy. The primary endpoint is objective response following the first course of therapy, using standard NANT response criteria. Secondary and other endpoints will include toxicity, site specific response, best response for patients treated with two courses of therapy (if applicable), overall survival, and correlative biology endpoints related to radiation exposure. Up to a total of 105 eligible and evaluable patients will be randomized to one of the three arms.

[figure not shown]
Hypothesis:

We hypothesize that:

- ¹³¹I-MIBG, combined with either vorinostat or irinotecan, will be associated with a higher objective response rate compared with single-agent ¹³¹I-MIBG;
- ¹³¹I-MIBG, combined with either vorinostat or irinotecan, will be tolerable but associated with an increase in protocol-associated toxicity compared with single-agent ¹³¹I-MIBG;
- ¹³¹I-MIBG, combined with either vorinostat or irinotecan, will be associated with increased measures of radiation exposure as assessed by peripheral blood markers.

TREATMENT SCHEMA

Patients will be randomized at study entry to one of three treatment arms.

Patients assigned to single-agent ^{131}I -MIBG (Arm A) will receive 18 mCi/kg ^{131}I -MIBG on Day 1 and autologous stem cell infusion on Day 15.

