10.0 STATISTICAL CONSIDERATIONS

10.1 Pick-the-Winner Design

Up to a total of 105 eligible and evaluable patients will be randomly assigned to one of the 3 MIBG arms. At completion of the study, the regimen with the highest observed response rate (by central review of response) after one course of therapy will be selected as the “winner” – i.e. the regimen that will be recommended as the MIBG backbone for future studies – provided that toxicity, tolerability, and other considerations confirm the feasibility of the regimen.

Two interim analyses for futility (to drop an inferior arm) will be undertaken: after 60 patients (approximately 20/arm) and after 81 patients (approximately 27/arm) have been randomized and completed at least one course and deemed evaluable for response. This analysis will be performed initially using site report of response. The following rule will be applied: if one of the arms is clearly inferior to the other two, then consideration will be given to dropping that single regimen. Study accrual will not pause while awaiting the results of any interim analysis (see below for modification per Amendment 7A). However, study accrual will be halted if needed to complete central review of response prior to dropping any regimen. The criterion to be used is based on Bayesian posterior probabilities (see Appendix VIII).

In addition, if one arm is dropped at the time of the 1st interim analysis, then after 35 patients have been randomized to each of the remaining arms and evaluated after the 1st course, we will compare these 2 remaining arms based on site report of response. If one arm is not clearly superior according to Bayesian posterior probabilities, accrual will continue until 42 evaluable patients per remaining arm have been randomized (yielding total sample of 104 patients in this scenario).

If neither futility rule is met, accrual will continue until 35 patients/arm are eligible and evaluable, for a total of 105 patients. With Amendment 7A, the design was modified to apply stochastic curtailment principles to permit early selection of a winner (see below). In order to account for potentially ineligible or inevaluable patients, a maximum of 115 patients are anticipated to enroll to yield 105 eligible and evaluable patients.

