10.5 Sample Size and Study Duration

While we expect that both the vincristine/irinotecan and the vorinostat arms will demonstrate higher response rates compared to the MIBG-alone arm – and that the selection therefore will only involve those

two arms – we have included the MIBG-alone arm to calibrate the improvement and better understand the impact of these chemotherapy additions. However, for purposes of determining the number of required patients, we will consider that all three arms are candidates of selection (i.e. could result in the highest observed response rate). The number of patients (35 per MIBG regimen, if no arms are dropped as inferior) was calculated to ensure an 80% chance that the regimen with the highest response rate is selected – if in fact that response rate is at least 15% better than the other two (using the methods described by Sobel and Huyett¹¹⁴ and summarized by Bechhofer, Santner and Goldsman¹¹⁵). Because we have incorporated Bayesian criteria for dropping an inferior arm or stopping early, the power of correct selection and other design characteristics were determined by simulation (see Appendix VIII for more details).

Table A in Appendix VIII summarizes the probability of correct selection, the probability of dropping one arm for futility, the probability of dropping the superior arm for futility, and the average number of patients in the inferior arm.

Estimates of the number of available patients for this study are derived from previous ¹³¹I-MIBG studies at NANT ¹³¹I-MIBG institutions. Specifically, NANT01-02 accrued 50 patients with refractory disease over approximately 40 months of active patient recruitment. NANT04-06 accrued 26 patients with relapsed or refractory disease over the approximately 40 months during which that study was open. This accrual rate underestimates the number of available patients given that NANT04-06 was a phase I study that utilized a 3+3 dose escalation strategy and accrual was closed for a minimum of 6 weeks after the third patient at each dose level was treated. CHOP, Cincinnati Children's, UCSF, and the University of Michigan treat 25, 12, 12, and 7 patients per year on their respective expanded access ¹³¹I-MIBG protocols. Newer NANT MIBG centers now include Children's Hospital Boston, Cook Children's Hospital, Children's Hospital of Colorado, Hospital for Sick Children, and Seattle Children's Hospital. These newer centers will increase access to MIBG treatment slots.

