APPENDIX VIII. Interim Analyses using Bayesian Rules

A.1 Overall Trial Design

The pick-the-winner design includes the following three analyses (displayed in schematic below)

- Perform interim analyses after 60 and 81 patients have been treated and evaluated. The goal of these analyses will be to drop an inferior arm, if indicated, as well as to review the toxicities
- Perform the final analysis after 105 patients have been treated and evaluated, with one exception:
 - if an arm is dropped as inferior after 60 patients, then the remaining 2 arms will be analyzed and compared after 35 patients are evaluable in those arms. If the results are clear-cut, and one arm is superior, then the trial will stop; otherwise accrual will continue until 104 patients (42 in the 2 remaining arms) are randomized and evaluated.

A.2 Methods Used for Establishing the (Bayesian) Rules for Dropping the Inferior Arm or Selecting the Superior Arm

A.2.1 Notation and Distributions:

At any given time in the trial,

- let X_A , X_B , and X_C represent the number of responders observed for regimens A (=MIBG alone), B (=MIBG + vincristine + irinotecan), and C (MIBG + Vorinostat), respectively,
- let n_A , n_B , and n_C represent the total number of patients evaluated for response in arms A, B, and C, respectively,
- and let p_A , p_B , p_C denote the (true) probability of response (i.e. response rates) for regimens A, B, and C.

Thus X_A , X_B , and X_C are binomial random variables with parameters p_A , p_B , p_C , and n_A , n_B , and n_C .
NANT 2011-01 Version Amendment #8 01-10-2018 120

The Bayesian methodology says that p_A , p_B , p_C are not fixed numbers, but rather have a distribution, or range of possible values. So we modeled these distributions as beta with parameters α and β . For our calculations, we will assign the same mean value of 0.20 for all three distributions – but with very little confidence. So for each p (which will be the same for each p_A , p_B , p_C , separately)

$$p \approx \text{Beta}(\alpha, \beta)$$

where $\alpha/(\alpha+\beta)=0.20$ is the mean of the distribution and $\alpha+\beta=1.0$ is like the “sample size”.

We call this our prior distribution of p and p_A , p_B , p_C .

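### Section 10.7.1 names no arm term when it relates whole-body dose to response or toxicity, so a sensitizer that shifts both could create or hide a dose association

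*Combined protocol and SAP*

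**What the plan says.** The primary analyses in Section 10.7.1 will "compare whole body radiation dose between randomized treatment groups and also between responders vs. non-responders using analysis of variance". Its secondary analyses compare dose between patients with and without grade 4 neutropenia, grade 4 thrombocytopenia, and grade 3 or higher non-hematologic toxicity. Section 2.6.1 lists the same comparisons. Neither section names an arm factor, stratification or covariate for the responder or toxicity comparisons.

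The protocol treats both possible arm effects as live:

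- **Arm and dose.** Section 2.6.1 says that "it is not clear whether the addition of irinotecan or vorinostat might impact whole body radiation dose", and names two mechanisms: greater tumor uptake or retention of ¹³¹I-MIBG, and slower physiologic clearance.
- **Arm and outcome.** The hypotheses after the abstract say that ¹³¹I-MIBG with either sensitizer "will be associated with a higher objective response rate compared with single-agent" treatment. They also expect more toxicity on the combinations.

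Section 10.7.3 plans logistic models of response and of toxicity that contain both randomized arm and whole-body exposure. These are built around each blood biomarker in an optional sub-study. Section 10.7 opens by calling the correlative biology studies descriptive, and Aim 1.5 (dose by regimen) is exploratory.

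**The concern.** Whole-body dose and response are both measured after randomization. If the arms differ on both, responders come disproportionately from the arm with the higher response rate. Their mean dose is then pulled toward that arm's mean, even when dose and response are unrelated within every arm. The same holds for toxicity: irinotecan and vorinostat cause cytopenias and diarrhea in their own right (Sections 6.1.9 and 6.5).

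Section 2.6.1 says that the effect of whole-body dose on response is unresolved, so this comparison will be read as evidence on that question. Without an arm term it can report an arm difference as a dose association. If an arm raises response but lowers dose, it can hide a real one.

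**Working it through.** **The plan's own figure.** Section 10.7.1 gives no sample size or power. The only ANOVA power stated in Section 10.7 is in 10.7.3: 91% with 28 per arm, a 0.05-level F-test, and largest minus smallest mean equal to 1 SD. With means (-0.5, 0, +0.5) SD, the noncentrality is λ = 28 × (0.25 + 0 + 0.25) = 14 on 2 and 81 df. Power is 0.918, so the figure reproduces.

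**Inputs**

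- Patients per arm: 35, if no arm is dropped ("accrual will continue until 35 patients/arm are eligible and evaluable", Section 10.1). Section 10.7.1 plans dosimetry for all patients.
- Base response rate: 20% ("we will assign the same mean value of 0.20 for all three distributions", Appendix VIII). As a check, 36%, the single-agent rate in the abstract.
- Response gain: 15 points ("if in fact that response rate is at least 15% better than the other two", Section 10.5).
- Dose spread: in 53 patients at 18 mCi/kg, "the median estimated whole body radiation dose was 292 cGy, with a broad range of 173 – 418 cGy" (Section 2.6.1). No SD is given. The range is 418 - 173 = 245 cGy. Dividing by 4.54, the expected range in SDs of 53 normal values, gives 54 cGy. Dividing by 4 gives 61 cGy.
- Assumed, not in the documents: two-sided alpha 0.05, and dose shifts of 0.25, 0.5 and 1 SD.

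**Size of the spurious difference.** With equal arms, response rates pᵢ and dose shifts sᵢ, and no within-arm link, the expected responder minus non-responder difference is Σpᵢsᵢ/Σpᵢ - Σ(1-pᵢ)sᵢ/Σ(1-pᵢ). For rates (0.20, 0.20, 0.35) and a 1 SD shift in the third arm:

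0.35/0.75 - 0.65/2.25 = 0.467 - 0.289 = 0.178 SD

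That is 9.6 cGy at SD 54 and 10.9 cGy at SD 61. A 0.5 SD shift gives half: 0.089 SD, or 4.8 to 5.4 cGy.

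**False-positive rate.** Simulation of 40,000 trials per setting: dose normal with an arm shift, response Bernoulli with an arm rate, the two independent within arm. The unadjusted test has 1 and 103 df; the test with arm has 1 and 101 df.

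| Setting | Unadjusted | With arm |
|---|---|---|
| Only dose differs (1 SD) | 5.0% | 5.1% |
| Only response differs (20% to 35%) | 5.1% | 5.1% |
| One arm: 20% to 35%, +0.25 SD | 5.5% | 5.1% |
| One arm: 20% to 35%, +0.5 SD | 6.8% | 5.1% |
| One arm: 20% to 35%, +1 SD | 11.2% | 5.1% |
| One arm: 20% to 35%, -1 SD (spurious inverse link) | 11.6% | 5.1% |
| Both sensitizer arms: 20% to 35%, +0.5 SD | 6.3% | 4.9% |
| Both sensitizer arms: 20% to 35%, +1 SD | 10.0% | 4.9% |
| One arm: 36% to 51%, +0.5 SD | 6.2% | 4.8% |
| One arm: 36% to 51%, +1 SD | 9.3% | 4.8% |

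**Toxicity.** Section 2.2 reports 22% grade 3 and 9% grade 4 non-hematologic toxicity at 18 mCi/kg, taken here as 31% in total. If one arm rises to 50% (assumed) with a 1 SD dose shift, the unadjusted rate is about 13% against about 5% with arm.

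**Masking.** Take a true within-arm difference of 0.6 SD (assumed) and response 20% to 35% in one arm. If that arm lowers dose by 0.5 or 1 SD, unadjusted power is about 58% or 40%, against about 73% with arm. With no dose shift, power is about 75% unadjusted and 73% with arm, so the arm term costs about 2 points.

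**The case against.** The strongest reply has four parts.

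1. **The plan never says that the arms are pooled.** A reader might infer that it does. The sentence names treatment group and responder status together, and a two-factor ANOVA fits the wording. This stands: what can be said is that arm is not specified. Section 10.7.3 does list arm explicitly where adjustment is meant, so the silence needs resolving.

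2. **A dose link need not be false.** A reader might infer that any association produced by an arm difference is an artefact. The documents do not support that. One mechanism in Section 2.6.1, greater tumor uptake or retention, could plausibly raise response as well, so dose may partly mediate the arm effect. An arm term would then remove real information. This stands, and it is the reason to keep the unadjusted result. It does not justify reporting that result alone, because the rationale in Sections 2.3.2 and 2.4.3 (impaired DNA repair) is a route other than dose.

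3. **Models with arm and dose are already planned.** Section 10.7.3 has them, with at least 80% participation expected. They do not replace 10.7.1: they also adjust for biomarker change, and they cover about 84 of 105 patients.

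4. **The stakes are low.** The work is exploratory, 10.7.1 states no alpha, no dose shift is documented, and the winner is chosen on response rate subject to toxicity, tolerability and other considerations (Section 10.1). This stands, and it limits the point to a minor one.

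A reader might also infer a much larger inflation. A 20-point gain (20% to 40%) with a 1 SD shift gives 15.5%, but that exceeds the 15-point difference used to size the trial.

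**Conclusion.** The point holds as a minor gap in specification. Section 10.7.1 should say how arm enters the responder and toxicity comparisons. If arm is left out, and one arm changes dose and also changes the outcome by another route, the comparison is biased in either direction. At the design difference the false-positive rate rises by about 2 points (0.5 SD shift) or 6 to 7 points (1 SD), so a false association becomes somewhat more likely but is far from certain. Both dose and outcome must differ by arm for the spurious association to have a systematic direction.

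The percentages rest on the assumed alpha, the assumed dose shifts and no within-arm link. The cGy figures also rest on the assumed SD. Selection of the winning arm is unaffected.

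**What to change.** In Section 10.7.1, state that the responder versus non-responder comparison and each toxicity comparison include randomized arm as a factor. Report the within-arm pooled difference in dose with its 95% confidence interval, and show the unadjusted difference beside it, noting that dose may partly mediate the arm effect.

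This is about one sentence of text and needs no new data. It uses two degrees of freedom and costs about 2 points of power when arm is irrelevant.
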